#### **3.2. Primary or secondary safety endpoints:**

There are no safety endpoints in this study.

### **4. Drugs, Devices and Biologics**

#### **4.1. Manufacturer and name of all drugs, devices and biologics:**

The mobile medical application, iCanCope with Pain was developed by The Hospital for Sick Children in Ontario, Canada.

#### **4.2. Description and purpose of all drugs, devices and biologics:**

The iCanCope with Pain is a smartphone app to help young people manage persistent pain. It is comprised of personalized goal setting to improve pain and function, CBT-based pain self-management training and rehearsal, and peer-based social support through a closed online community for youth with SCD. The app provides users with reminder and positive feedback on their progress to reaching their goals. The app will provide in-the-moment access to pain coping strategies to promote positive changes in mood, behavior, and pain. The app will also allow youth to track their symptoms in real-time and generate customized reports from their data to show clinicians. The parameters that will be tracked by the app include pain, pain impact, mood, and sleep. The app will use the diary input to push relevant advice to the user.

#### **4.3. Regulatory status of all drugs, devices and biologics:**

This study will be testing the initial effectiveness of the iCanCope app and website. These tools meet the definition of device because they intended to be used in the mitigation of disease. Per information found in the FDA published guidance for Mobile Medical Applications, this 'device' would be one for which the FDA would intend to exercise enforcement discretion - (meaning the FDA will not intend to enforce requirements under the FD&C Act and an IDE will not be needed for the study).

**4.3.1. Drugs or Biologics:**

IND Exempt. Explain: [Click here to enter text.](#)  
 IND.

**4.3.2. Devices:**

IDE Exempt. Explain:  
 Abbreviated IDE / Non-Significant Risk. Explain: [Click here to enter text.](#)  
 IDE / Significant Risk.

**4.4. Plans to store, handle, and administer any study drugs, devices and biologics so they will be used only on subjects and be used only by authorized investigators:**

N/A

**5. Procedures Involved**

**5.1. Study design:**

A multi-site parallel group pilot RCT of *iCanCope with Sickle Cell Pain* versus *Attention Control Education* will be conducted with 160 youth (age 12-18) with SCD and their caregiver. The sites will include Emory/CHOA, The Hospital for Sick Children, and Connecticut Children's Medical Center, University of Mississippi, University of Florida, Boston Medical Center, Ann & Robert H. Lurie Children's Hospital of Chicago, Nationwide Children's Hospital, C.S. Mott Children's Hospital and Seattle Children's Hospital. Participants will be randomized into one of two groups; experimental group or attention control group. The intervention phase will last 6-8 weeks, with participants given a maximum of 12 weeks to complete the intervention content. This treatment period is based upon the typical duration of chronic pain intervention trials. Outcome assessment will occur at baseline (T1), immediately after completion of the intervention (2 months; T2), and repeated at 6 months post-intervention (T3) to allow for assessment of maintenance of treatment gains as youth with SCD may have fluctuations in their disease course that influence pain outcomes.

**5.2. Research procedures:**

Experimental Group

In addition to standard medical SCD care, youth will receive the *iCanCope with Sickle Cell Pain* intervention over a period of 6 to 8 weeks. Participants will be given a maximum of 12 weeks to complete the program if delays occur. The web and app intervention will be delivered on restricted password-protected applications that will allow us to track user engagement (detailed user level and aggregate analytics). Youth will be encouraged to log onto the app (via push notifications) to track their symptoms, develop and track functional goals, access coping strategies, and socially engage in the *iCanCope* community. Youth and their caregiver will also be encouraged to access the *iCanCope* website, which will contain interactive SCD education and self-management strategies. The youth website will be organized into 6 core modules and 2 optional\*\* modules, participants will complete one module per week (Table 3). Delivery of the optional modules will be based on response to the baseline measures. See Table 5 for a list and

description of all study measures. Eligibility to receive the optional insomnia module will be based on insomnia symptoms evaluated using two questions from the Adolescent Sleep Wake Scale (ASWS) assessing difficulty falling asleep ("I have trouble going to sleep") and difficulty maintaining sleep ("After waking up during the night, I have trouble going back to sleep"). Adolescents responding "quite often," "frequently, if not always," or "always" to either of these will be judged to have symptoms of insomnia, and receive the module. Eligibility for the optional negative emotions module will be determined by the baseline score on the 4-item PROMIS depressive symptoms scale, with a score of 9 or higher indicating eligibility to receive the optional module. Eligibility for the optional modules will be sent via secure email to SickKids from Seattle Children's. Children's staff will only indicate "yes" or "no" if they meet the criteria for the PROMIS and ASWS measures. There will also be content designed for caregivers to provide instruction in the best ways to support youth's pain management skills and encourage adaptive coping, divided into six modules (Table 3).

\*\*optional modules for this study are potentially two additional modules that would be given to youth only if they are randomized to Group A and if their baseline scores qualify them for one or both of them. This is not optional, but an addition to their modules, similarly to how branching logic works.

**Experimental Group Semi-Structured Interviews:** Following the completion of the iCanCope with Sickle Cell Pain program, youth and parent participants will be invited to participate in a semi-structured interview over the phone with the research staff from SCRI. The interviews will be conducted any time between the post-treatment (T2) and 6 month follow up assessment (T3). All participants that are within the timeframe stated above will be asked to participate. The semi-structured interview will allow participants to qualitatively comment on the intervention. The research staff will follow a semi-structured interview guide with questions pertaining to their experience using the iCanCope with Sickle Cell Pain website and app (see attached guides in supporting documents). The interview will be audio-recorded and a research staff will transcribe the interview verbatim. The research staff will be trained on how to transcribe the interview and a different staff member will double check the transcription.

The semi-structured interviews will determine (i) participants' acceptability of and level of engagement in the iCanCope with Sickle Cell Pain program and (ii) their likes and dislikes of program, and improvements on the program content and design. The research staff will verify transcripts against the tapes and field notes taken during the interviews will be transcribed and included in the analytic process. All data will be read by multiple independent coders to obtain an overall understanding of the data and develop themes based on the research questions. This data will be used to refine the iCanCope with Sickle Cell Pain program for future trials.

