#### Attention Control Group

The control group is designed to account for potential effects on outcomes of time, attention, as well as computer use during the intervention period. In addition to standard medical care, youth in the attention control group will be provided with access to a self-guided education study website, called the Sickle Cell Library, which will contain static education about SCD (no self-management skills, goal-setting, or social support content). Any site links will be monitored weekly to ensure that they do not add any “active ingredients” during the trial. We have completed a 2015 scoping review of existing SCD patient education websites (see above) to identify content to include in the control site. The control condition will be delivered over 8 weeks on a restricted password-protected platform that will allow us to track usage and engagement similar to the experimental group. Participants will be encouraged to log onto the control website and complete all study outcome assessments online at the same time intervals as the experimental group. Participants in the control group will receive 4 check-in contacts (once every 2 weeks) by their preferred contact method to make sure they are not having any issues with the website and remind them to review content.

Table 4. Control Website Content for Teens and Parents: Sickle Cell Library		
Section Number	Title	Education Content
1	Introduction	Intro to program
2	About sickle cell disease	What is SCD, symptoms and complications
3	Treatments and medication	About medications, transfusions, pain medications, complementary medicines
4	Acute and chronic pain	Acute pain, chronic pain, factors that influence pain experience

5	Healthy lifestyle	Diet, exercise, alcohol and drugs, school and hospital stays
6	Looking ahead and research	Transition to adult care, clinical research

Both Groups

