**5.4. Data to be collected, including long-term follow-up data:**

Outcome data are self-report and will be collected online using the study website (Table 5). All measures have evidence of reliability and validity in youth in this age range, and include the core measures recommended for pain clinical trials. T1 = pre-treatment; T2 = post-treatment (2 months); T3 = follow-up (6 months post-treatment).

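### The interview offered only to iCanCope families falls between T2 and T3, so the 6-month outcomes follow a research contact that control families do not get

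*Combined protocol and SAP*

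**What the plan says.** Section 5.2 contains a block titled "Experimental Group Semi-Structured Interviews". After programme completion, "youth and parent participants will be invited to participate in a semi-structured interview over the phone with the research staff from SCRI". On timing: "The interviews will be conducted any time between the post-treatment" assessment (T2) and the 6-month follow-up (T3). On coverage: "All participants that are within the timeframe stated above will be asked to participate". The guide has "questions pertaining to their experience using the iCanCope with Sickle Cell Pain website and app". The stated use of the material is to improve the programme for later trials.

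The control-arm part of Section 5.2 states: "The control group is designed to account for potential effects on outcomes of time, attention, as well as computer use during the intervention period". Control families receive four staff check-ins, one every two weeks, during their 8-week programme. Neither that part nor the text on both groups gives them an interview or a matched contact after T2.

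T3 matters to the trial's claims. Section 5.1 includes it "to allow for assessment of maintenance of treatment gains", and Section 1.2 hypothesises an advantage over control both post-treatment and at 6 months. Section 5.4 says: "Outcome data are self-report and will be collected online". Section 14.1 does not mention the interview.

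**The concern.** A one-to-one call with coordinating-centre staff about a pain self-management programme could act on later self-report in several ways. It could bring the coping skills back to mind, add personal attention, change how the family answers, or keep the family engaged through follow-up. The documents describe none of these effects. They are possibilities that a well-matched control would normally neutralise.

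Here they are not neutralised at T3. The contact goes to one arm only, it precedes the T3 measures, and no blinding of participants is described. A 6-month difference, or the lack of one, could then reflect what remains of the programme, what the interview did, or both. T3 is the trial's only assessment of durability.

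**Working it through.** The plan states no figure on this point, so the check is a comparison of its sections.

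1. **Which arm.** The block's title names the experimental group, and the questions concern iCanCope, which control families do not receive. No sentence expressly excludes controls. The restriction follows from the title, the content and the absence of a control counterpart.

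2. **Order of events.** T2 comes first, then the interview window, then T3. Every interview held as planned comes after that family's T2 and before its T3. T2 data cannot be affected.

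3. **Matching contact.** The four control check-ins lie inside the 8-week control period, before T2. Reminders, staff access and the contact at each time point (Sections 5.2 and 20.4) apply to both arms. Between T2 and T3, the interview is the one staff contact planned for a single arm.

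4. **Which analyses lie downstream (Section 14.1).**
   - The explicit Aim 1 group-by-time interaction compares change from pre-treatment to post-treatment. It is not exposed.
   - The baseline-to-6-month contrasts, stated for each group, are exposed in the experimental arm.
   - The 6-month between-group hypothesis of Section 1.2 is exposed. So is any secondary-outcome or longitudinal model that uses T3 data.

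5. **Can the analysis separate the two?** Let *m* be the programme's own effect at T3, *u* the share of experimental families with T3 data who were interviewed, and *d* the mean effect of the interview on their T3 score. With no control family interviewed,

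   expected T3 difference = *m* + *u* × *d*.

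   The between-arm comparison estimates only the sum. Comparing interviewed with non-interviewed experimental families does not recover *d*, because families choose whether to take part. The GEE in Section 14.1 has no term for the interview, and adding one would not remove this self-selection.

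6. **Can *u* or *d* be filled in?**
   - Numbers: 160 / 2 = 80 dyads per arm if allocation is 1:1 (an assumption), and 80 × 0.8 = 64 after the 20% attrition in Section 10.4. These bound who might be asked. They do not count who is interviewed.
   - Uptake: Section 2.2 reports interviews with 8 dyads in a Web-MAP pilot of 12 youth, but not how many were invited, so it gives no acceptance rate.
   - Effect: the documents give no value for *d*, and no sign.

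The asymmetry follows from steps 1 to 3 alone. Its numerical consequence cannot be calculated.

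**The case against.** **The exposure is partial.** Only families who have completed the programme and are in the window are asked, and they may decline. This stands. A reader might infer that all 64 retained experimental dyads are exposed by plan, but the documents support an invitation, not an exposure. Partial uptake shrinks *u* and leaves the contact one-sided.

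**The mechanism is inferred.** The interview asks about acceptability, engagement, likes, dislikes and improvements. Nothing says that it rehearses skills or hints at wanted answers, and asking for dislikes cuts against the latter. The guides are not in the documents, T3 is completed online rather than reported to the interviewer, and the call may come almost 6 months before T3. All this stands. A reader might infer a bias in favour of iCanCope, but the documents do not establish a direction.

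**The size may be trivial.** A reader might assume 50–100% uptake and a shift of 0.1–0.3 pain-scale points, giving 0.5 × 0.1 = 0.05 to 1.0 × 0.3 = 0.30, and divide by the 0.75 in Section 10.4 to get 7–40%. That figure should not be used:
- The 0.75 is averaged over three assessments. A T3-only shift moves that average by a third as much, 0.017 to 0.10, or 2–13%.
- Both inputs are assumptions, and the range leaves out zero.
- At SD 2, 0.3 points is 0.15 SD. That is 0.15 / 0.41 = 37% to 0.15 / 0.285 = 53% of the pooled effects that Section 2.3 quotes for whole internet programmes.
- Section 3.1 names pain-related disability, not pain intensity, as the primary endpoint.

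**Controls also get attention.** Their four check-ins have no stated iCanCope equivalent, so which arm has more contact overall is not established. This stands, but it concerns the intervention period and does not offset a contact between T2 and T3.

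**Earlier interviews serve their purpose better.** Recall is fresher, and families later lost to follow-up can still be heard. This is a fair trade-off in a pilot. It bears on the cost of the fix, which is designed to limit that loss.

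**Conclusion.** The concern holds in a limited form. The plan places a voluntary staff contact, offered to experimental families only, before the self-reported T3 outcomes. It thereby leaves the 6-month between-group comparison and the maintenance assessment open to a second explanation that the planned analysis cannot remove. This rests on the text of Sections 1.2, 5.1, 5.2, 5.4 and 14.1, and on reading the interview as experimental-arm only, which its title and content support.

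It does not extend to T2 or to the explicit pre-to-post interaction. No size or direction of bias at T3 can be given, and the effect may be nil. The point does not show that a T3 result would be wrong, only that it would be harder to interpret for an avoidable reason. It ranks as a cheap improvement.

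**What to change.** In Section 5.2, replace the T2-to-T3 interview window with a rule tied to T3: each experimental family is interviewed only after its T3 questionnaires and 7-day diary have been submitted, or after its T3 window has closed. The section gives no closing date for T3, so the rule needs one. Families who withdraw from follow-up before T3 and still agree to talk may be interviewed at withdrawal. They contribute no later T3 data, so that interview cannot affect the comparison, and their views are kept. For any family already interviewed before T3, retain the interview date and report the number alongside the T3 results.

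The cost is a sentence or two and a scheduling rule, with no added staff or procedures. Recall of the programme will be up to about 6 months older. The Treatment Evaluation Inventory at T2 and the platform's engagement data partly offset this, although a brief acceptability scale does not replace an open interview. Families lost without contact may still be missed.

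The last interviews finish a few weeks later. With an assumed 4-week interview period, the longest course is 12 weeks (about 2.8 months) + 6 months + 4 weeks (about 0.9 months), or about 9.7 months. That is roughly within the 10 months in Section 8.1, before any allowance for late T3 returns.

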**Table 3. Youth Intervention Web Content: *iCanCope with Sickle Cell Pain***

Module Number	Module Title	Content/Skills
1	Introduction	Intro, SMART Goals, 3Ps pain, types of psychological treatments
2	Managing stress	Reduce negative thoughts: replace with positive and thought stopping
3	Relaxation	Relaxation: deep breathing, muscle relaxation, imagery, mini relaxation
4	Sleep	Pain and sleep, healthy sleep, ways to fall and stay asleep

5	Communication and self-advocacy	Communication skills, talking with healthcare team and school
6	Healthy lifestyle	Pacing, graded activity, hydration
7	Optional: Insomnia	Think differently about sleep, more falling and staying asleep strategies
8	Optional: Negative emotions	Identify negative emotions, schedule pleasant activities, find the positives.
Parent Intervention Web Content		
Module Number	Module Title	Content/Skills
1	Introduction	What your teen will learn, SMART goals to support your teen
2	Behavioral plans	Behavioral plans
3	Problem solving 1	Bright IDEAS problem solving system
4	Problem solving 2	Bright IDEAS problem solving system
5	Communication	Strategies that can help you talk and listen to your teen, strategies to communicate with health care providers and school staff
6	Wrap-up	Review

#### Attention Control Group

The control group is designed to account for potential effects on outcomes of time, attention, as well as computer use during the intervention period. In addition to standard medical care, youth in the attention control group will be provided with access to a self-guided education study website, called the Sickle Cell Library, which will contain static education about SCD (no self-management skills, goal-setting, or social support content). Any site links will be monitored weekly to ensure that they do not add any “active ingredients” during the trial. We have completed a 2015 scoping review of existing SCD patient education websites (see above) to identify content to include in the control site. The control condition will be delivered over 8 weeks on a restricted password-protected platform that will allow us to track usage and engagement similar to the experimental group. Participants will be encouraged to log onto the control website and complete all study outcome assessments online at the same time intervals as the experimental group. Participants in the control group will receive 4 check-in contacts (once every 2 weeks) by their preferred contact method to make sure they are not having any issues with the website and remind them to review content.

Table 4. Control Website Content for Teens and Parents: Sickle Cell Library		
Section Number	Title	Education Content
1	Introduction	Intro to program
2	About sickle cell disease	What is SCD, symptoms and complications
3	Treatments and medication	About medications, transfusions, pain medications, complementary medicines
4	Acute and chronic pain	Acute pain, chronic pain, factors that influence pain experience

5	Healthy lifestyle	Diet, exercise, alcohol and drugs, school and hospital stays
6	Looking ahead and research	Transition to adult care, clinical research

Both Groups

Both groups will complete baseline (T1) measures online prior to randomization. Participants will be randomly allocated to either the experimental (*iCanCope with Sickle Cell Pain*) or attention control education group. Following program completion at 2 months (T2), participants will be asked to complete post-test measures. Electronic and SMS text reminders will also be sent by the study team. Participants will be asked to complete the same measures at 6 months (T3) following completion of the intervention or control condition. All measures will be completed online, either at home or in clinic. Paper versions of measures will be available if online access is not possible. Participants in both groups will be able to contact staff for technical problems with the app or website. Research staff will also be available at routine clinic visits during the study period.

**5.3. Data sources that will be used to collect data about subjects:**

Table 5. Study Measures					
Measure	Description of Measure P=parent report, T=teen report	Time to Complete	T1	T2	T3
	Screening and background measures				
Sickle Cell Pain Burden Interview (SCPBI)	The SCPBI will be used to screen for SCD pain burden.  (P, T)	2-3 minutes	X	X	X
Background questionnaire	This questionnaire will assess sociodemographic variables (including family income), pain characteristics such as intensity, location, and temporal features (T) and access / use / comfort with smartphones and internet technology. (P, T)	5 minutes	X		
Treatment expectancies questionnaire	7-item questionnaire to rate treatment expectancy. (P, T)	3 minutes	X		

Adolescent Sleep Wake Scale	2 items from the questionnaire will be used to screen for the optional website intervention module on insomnia.  (T)	1 minute	X		
	Primary outcome measures				
Daily pain diary (7 day)	Pain intensity (NRS-11), location, and 9-item CALI.  Completed daily for 7 days (T)	3 minutes	X	X	X
Coping Strategies Questionnaire for Sickle Cell Disease (CSQ)	The CSQ  will assess use of different strategies to cope with pain (three primary scales: coping attempts, negative thinking, passive adherence).	15 minutes	X	X	X
	Secondary outcome measures				
PROMIS-25 v1.1 Pediatric Profile	The PROMIS Pediatric Profile will be used to assess physical and emotional functioning. This is a collection of short forms containing 4 items from PROMIS domains (Depressive Symptoms, Anxiety, Mobility, Pain Interference, Fatigue, and Peer Relationships).  (T)	10 minutes	X	X	X

	items comprise each subscale.  (P)				
Treatment Evaluation Inventory (TEI)	The TEI will be used to assess acceptability (P, T)	3 minutes		X	
Patient's Global Impression of Change Scale	Change in global health / quality of life.  (T)	2 minutes		X	X
Bath Adolescent Pain Questionnaire – for parents (BAPQ-P)	The BAPQ is a measure to assess social functioning, physical functioning, depression, general anxiety, pain specific anxiety, family functioning and development. (P)	15 minutes	X	X	X
Symptom Checklist - 90	The Symptom Checklist -90 assesses a range of psychological symptoms, including obsessive compulsive, depression, anxiety, etc. (P)	12-15 minutes	X	X	X
Adult Responses to Child Symptoms (ARCS)	This 13-item questionnaire assesses parent behavior including protectiveness, minimizing, and encouraging response to children's pain behavior. (P)	5 minutes	X	X	X
Client Service Receipt Inventory (CSRI)	SCD healthcare utilization.  (P)	10 minutes	X		X
Adverse events self-report assessment	Adverse event form will be used.	3 minutes		X	X

